9.6 Covariates

This study is designed to describe real-world outcomes associated with the use of efgartigimod. The covariates to be collected include any clinical characteristics, medication use, and medical procedures coded in the databases that could be used to provide a complete description of the cohorts and subpopulations. Baseline covariates observed in the patient’s medical history and other relevant factors prior to the study drug initiation will be assessed.

It is anticipated that not all variables can be collected in the three (3) selected databases; therefore, all covariates will be collected based on data availability. The following list of *a priori* covariates will be evaluated. A more detailed description of relevant covariates and their use in the analysis will be described in the SAP.

1. Cohort identification

- Date(s) of a diagnosis of MG (health care setting) to approximate disease duration (new-/old-onset)

2. Demographic factors

- Gender
- Ethnicity/race (if allowed)
- Patient's age at his/her index date
- Thymoma (with or without thymectomy), if present in database (date, indication, histology)
- [Supplementary variables]
 - Comorbidities
 - CCI will be calculated based on comorbidities identified in the lookback period in the selected databases.
 - Serological testing of MG diagnosis, if available
 - MG Disease severity, if available

3. Lifestyle variables⁴, if available

- Smoking
- Body mass index (BMI)
- Alcohol consumption

4. MG treatment

- Prior and current treatments, e.g.
 - Anticholinesterase agent
 - Corticosteroids
 - Chronic non-steroidal immunosuppressants
 - Monoclonal antibodies
 - Plasmapheresis/plasma exchange
 - IVIg therapy
- Duration of exposure of prior and current treatments, if available
- [Supplementary variables]

⁴ May only be available in EMR database(s) but not claims administration databases.

- Cumulative dose for each line of therapy, if available, and if not, number of distinct concomitant MG treatments (mono-, double or triple therapy)

5. Concomitant treatments

- Type of treatment and duration (for selected concomitant medications)
- [Supplementary variables]
 - Duration of exposure for each treatment
 - Cumulative dose of each treatment, if available

9.7 Subpopulations

Subpopulations with increased risk of malignancies will be established by reviewing all patient history in the lookback period, and will be defined as follows:

1. Elderly, age 65 years and older at their index date
2. Chronic use (i.e., ≥ 1 year) of corticosteroids

Lists of relevant codes will be included in the SAP.

10 Data sources

The study will be conducted using

- UK: CPRD
- France: SNDS
- US: Optum Market Clarity

10.1 Clinical Practice Research Datalink (CPRD)

Jointly sponsored by the Medicines and Healthcare Products Regulatory Agency and the National Institute for Health Research (NIHR), CPRD collects de-identified patient data from a network of general practitioner (GP) practices across the UK.

- Primary care data are linked to other health related data to provide a longitudinal, representative UK health dataset (e.g., linkage to Hospital Episode Statistics [HES]). Patient metrics include demographics (e.g., year of birth, gender, registration dates), medical history (e.g., event dates, diagnosis, symptoms, risk factors, comorbidities, referrals, laboratory results), prescriptions (e.g., prescription dates, therapeutic class, ingredient, dosage, duration), and clinical data (e.g., blood pressure, height, weight, immunizations, life habits such as smoking and alcohol use).
- HES data covers all National Health Service (NHS) Clinical Commissioning Groups in England including private patients treated in NHS hospitals and patients receiving care in treatment centres funded by the NHS. Each HES record provides a comprehensive picture about an individual admitted to an NHS hospital and their care, including

clinical information and diagnoses and procedures, dates of admission and discharge, and demographics include gender and ethnicity.

- There are >40 million patient lives in CPRD Aurum and >20 million patients in CPRD GOLD, including 15 million currently registered.
- For >30 years, research has informed clinical guidance and best practice, resulting in over 2,000 peer-reviewed publications.

10.2 Système National des Données de Santé (SNDS)

SNDS covers the entire population of France - 67 million residents. Each person is identified by a unique, anonymous number. Since 2006, SNDS has recorded information on all outpatient care (including drugs, imaging, and laboratory tests) and inpatient care (including diagnoses and procedures performed, coded according to the common classification of medical procedures—CCAM). The health expenditure for patients with long term diseases, such as cancer and diabetes, is fully reimbursed, and their diagnosis is recorded according to ICD-10 codes. SNDS has been extensively used in France to conduct real life studies, especially on the use, safety, and efficacy.

10.3 Optum Market Clarity

The Optum Market Clarity database includes deidentified data from medical and pharmacy claims and linked electronic health record (EHR) data for over 100 million unique, integrated patient lives from over 150 US payers, including commercial, Medicaid and Medicare plans. The database includes medical and pharmacy claims from United HealthCare, the largest insurer in the US, as well as partner claims from other insurers and clearinghouses. These claims are then linked with EHR data primarily from integrated delivery networks as well as some ambulatory networks. The database includes 20,000+ mapped clinical variables, diagnosis codes, signs and symptoms, biomarkers, laboratory and test results; it can also have natural language processing applied to unstructured clinical notes.

10.4 Coding Systems for CPRD, SNDS, and Optum

Table 2 below provides details on the diagnosis and medication coding systems for each of the 3 databases that will be used to conduct the study, as well as potential validity concerns.

Table 2. Coding system and potential validity concerns for CPRD, SNDS, and Optum

	Diagnosis	Medication	Potential Validity Concerns
CPRD	ICD-10 (HES) & medcode (CPRD) & SNOMED	Product code & medcode & OPCS (PLEX)	EMR system that captures physician recorded diagnosis, procedures. In general, data from CPRD are considered reliable.
SNDS	ICD-10	UCD (hospital) & CIP (retail) & CCAM procedures codes	The SNIIRAM has been largely recognised by the French authorities (INCa, HAS) as a powerful tool for epidemiologic studies. The main limitations are

			induced by the nature of the claims database, that require algorithms to increase the precision.
OPTUM	ICD-10 & ICD-9	CPT & HCPCS	A claim is limited to reimbursement purposes, therefore, algorithms may be required to increase the precision.

Abbreviations: CCAM = common classification of medical procedures; CIP = Code Identifiant de Présentation; CPT = Current Procedural Terminology; CPRD = Clinical Practice Research Datalink; EMR = electronic medical record; HAS = Haute Autorité de Santé; HCPCS = Healthcare Common Procedure Coding System; HES = Hospital Episode Statistics; ICD-10 = International Classification of Diseases, Tenth Revision (valid in 2024, revision valid at time of analysis will be used); INCa = French National Cancer Institute; OPCS = Office of Population Censuses and Survey; SNDS = le Système National des Données de Santé ; SNIIRAM = Système national d'information inter-régimes de l'Assurance maladie; SNOMED = Systematized Medical Nomenclature for Medicine; UCD = Unité Commune de Dispensation.

11 Study size

Statistical analysis in this study will be exploratory, and not aimed to confirm or reject predefined hypotheses. Instead of considering enrolled patients up-front at the start of study, sample size calculation is based on the number of patients included in the final analysis.

Since the variation under a random-effect model assuming heterogeneity across databases consists of both within-database and between-database variation and the number of patients will only impact the within-database variance, a two-step method for sample size calculation is conducted: 1) calculate the unadjusted sample size using inequality test assuming no heterogeneity among databases as if all patients were from one single database; 2) calculate the adjusted sample size by multiplying an adjustment factor to the unadjusted sample size assuming moderate heterogeneity. The feasibility of patient accrual based on projected cumulative number of patients in the databases is discussed considering factors that may impact the final number of patients, such as loss to follow-up, malignancy history, etc.

A real-world study using Optum database conducted by argenx showed malignancy incidence rate of 73.6 per 1,000 PY in MG population (data not published). An exploratory analysis using the result from the eculizumab Phase III study (NCT01997229) and its extension study (NCT02301624) ([Mantegazza 2021](#) and Results from clinicaltrials.gov) showed malignancy incidence rate of 42.0 per 1,000 PY for eculizumab-treated patients (data not published). With this wide range of observed incidences in MG populations, a spectrum of malignancy incidence rates was explored with upper and lower bound of 73.6 and 42.0 per 1,000 PY.

Under the fix-effect model assuming a common effect size and variance it is demonstrated that the variance of the combined effect will be the same regardless of the distribution of sample size in each database ([Borenstein 2010](#)). Therefore, the sample size calculation can be conducted based on the overall number of patients. Using a two-sided inequality test for two (2) Poisson rates ([Zhu 2017](#)) the unadjusted sample size is shown in Table 3 with 5% significance level, >85% power and rate ratio 1.3 under alternative hypothesis. The follow-up time is assumed to be 6 or

8 years based on the study design. The calculation is conducted using the power and sample size software PASS 2023. A total of 679 efgartigimod patients are needed assuming no heterogeneity (Power Analysis and Sample Size Software (2023) (NCSS, LLC. Kaysville, Utah, US [ncss.com/software/pass]).

To account for the increased variance owing to between-database variation under random-effect model if heterogeneity exists, the unadjusted sample size is multiplied by the adjustment factor of $1/(1 - I^2)$ (Wetterslev 2009) where I^2 is the heterogeneity measure. Assuming moderate heterogeneity of $I^2 = 0.5$ the adjustment factor equals to 2. The adjusted sample size is therefore two (2) times of the unadjusted sample size and shown in Table 3. A total of 1358 efgartigimod-treated patients are needed with a rate ratio of 1.3 under alternative hypothesis, 6-year follow-up and background rate of 42.0 per 1,000 PY to achieve >85% power.

Table 3. Sample size calculation

Background Rate in 1000PY	Follow-up Year	Rate Ratio under Alternative Hypothesis	Unadjusted Sample Size in Efgartigimod Cohort	Adjusted Sample Size* in Efgartigimod Cohort
42.0	6	1.3	679	1358
	8	1.3	509	1018
60.0	6	1.3	475	950
	8	1.3	357	714
73.6	6	1.3	384	768
	8	1.3	288	576

* Adjusted sample size = unadjusted sample size × 2, where 2 is calculated from $1/(1 - I^2)$ assuming moderate heterogeneity of $I^2 = 0.5$

To further demonstrate the ability to detect difference between two (2) cohorts, power analysis is conducted using two-sided inequality test (H_0 : rate ratio=1 vs. H_a : rate ratio \neq 1) for two (2) Poisson rates (Zhu, 2017) with 5% significance level and rate ratios of 1.2, 1.3, 1.4, 1.5, 2, 3 and 4. Table 4 shows that there are >80% power in most scenarios under the adjusted sample size of 1358.

Table 4. Power calculation

Background Rate in 1000PY	Follow-up Year	Rate Ratio under Alternative Hypothesis	Power
42.0	6	1.2	54.20%
		1.3	86.13%
		1.4	97.90%
		1.5	99.84%
		2	100.00%
		3	100.00%
		4	100.00%

Background Rate in 1000PY	Follow-up Year	Rate Ratio under Alternative Hypothesis	Power
	8	1.2	66.46%
		1.3	94.03%
		1.4	99.60%
		1.5	99.99%
		2	100.00%
		3	100.00%
		4	100.00%
60.0	6	1.2	69.45%
		1.3	95.36%
		1.4	99.76%
		1.5	100.00%
		2	100.00%
		3	100.00%
		4	100.00%
	8	1.2	81.34%
		1.3	98.76%
		1.4	99.98%
		1.5	100.00%
		2	100.00%
		3	100.00%
		4	100.00%
73.6	6	1.2	78.39%
		1.3	98.17%
		1.4	99.96%
		1.5	100.00%
		2	100.00%
		3	100.00%
		4	100.00%
	8	1.2	88.69%
		1.3	99.67%
		1.4	100.00%
		1.5	100.00%
		2	100.00%
		3	100.00%
		4	100.00%

It is anticipated that 829 and 681 cumulative efgartigimod-treated patients in UK and France up to year 2028, and 90% and 100% will be captured in the CPRD and SNDS databases, respectively. 1200 patients are anticipated in Optum database. Factors that may decrease the number of patients in the final analysis include inclusion/exclusion criteria, lost to follow-up, failure to match

to reference, no malignancy history in the look-back period, etc. Therefore, 30% of the patients in CPRD or SNDS are assumed to be excluded from the final analysis, and this percentage increases to 50% in Optum owing to higher loss-to-follow-up rate and shorter look-back period. A total of 1,599 efgartigimod-treated patients combining all 3 databases are anticipated to be included in the final analysis, which is greater than the sample size calculated above. Therefore, it is feasible to have sufficient efgartigimod-treated patient and achieve satisfactory power in the analysis.

Table 5. Anticipated efgartigimod-treated patients included in the final analysis

Database (Country)	Cumulative Patients by Country	% Captured in Database	Projected Patients in Database	% Included in Study	Sample Size in Each Database	Total Sample Size
CPRD (UK)	829	90%	746	70%	522	1,599
SNDS (France)	681	100%	681	70%	477	
Optum (US)	-	-	1,200	50%	600	

Abbreviations: CPRD = Clinical Practice Research Datalink; SNDS = le Système National des Données de Santé; UK = United Kingdom; US = United States.

12 Data management

Data management will be in accordance with the Sponsor’s designated contract research organisation (CRO)’s standard operating procedures (SOPs) regarding external data management which outline the procedures for establishing a data agreement, conducting a data intake analysis, performing data load and verification, executing data backups, defining data retention and destruction timelines. Additional SOPs may be applicable depending on the format of the data files to be delivered by the providers.

Furthermore, data protection and privacy procedures will be followed to ensure data files received from providers are processed for specific study purposes and only those requiring data access will have access to the data. This also ensures data are accurate and not kept longer than needed, and defines logical and physical data security standards which meet regulatory guidelines. Data transferred from the providers will be stored in a dedicated application instance for the MAH.

13 Data analysis

An SAP will be prepared once the protocol is approved by the EMA’s Pharmacovigilance Risk Assessment Committee (PRAC). The SAP will provide analytical methods that are applicable across all databases, as well as addressing database-specific differences that may need to be applied. These differences may include conventions for handling specific data elements of interest that define exposure, diagnoses, covariates, and subpopulations of interest.

More specifically, descriptive statistics will be used to analyse baseline demographic information, co-morbid conditions, and concomitant medication use. For each outcome of interest, the IR, with 95% CIs, will be calculated. IRs will be calculated within each individual database by dividing the number of events for each outcome by the total person-time at risk. A Poisson distribution will be assumed to compute 95% CIs for IRs.

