9.1 Study design

This multinational, longitudinal database cohort study will identify patients who are newly treated with efgartigimod and have a diagnostic code for MG (efgartigimod cohort). A patient will be considered an efgartigimod exposed patient if he/she has received at least one (1) dose of efgartigimod.

For each patient entering the efgartigimod cohort, the date of the first efgartigimod exposure in the database (either through an IV infusion or SC injection) will be their index date for the study. Only new users of efgartigimod will be included in this cohort, that is, a patient who receives a first prescription, or first dispensing, or has a first procedure code for efgartigimod during the study period and without a prescription or a dispensing or a procedure code for efgartigimod in the previous 12 months.

A reference cohort will also be selected with a 2:1 ratio to the efgartigimod cohort to provide an overall, real-world assessment of malignancy risk in patients receiving efgartigimod. The reference cohort will consist of patients with a diagnosis code for MG without efgartigimod exposure but is on any other therapy for the treatment of MG during the study period. The index date for each patient in the reference cohort will be assigned as the same index date as the corresponding matched efgartigimod patient.

Identification of patients in the reference cohort will be based on selected matching variables in the patient's history (prior to and including the index date) or within 6 months of the index date. More specifically, within each database, efgartigimod initiators will be matched 2:1 (reference: efgartigimod) by (1) age at index date (+/- 5 years), (2) sex, (3) Charlson Comorbidity Index (CCI)² and (4) duration of prior use of other MG treatment as matching variables prior to and including the index date or within 6 months of the index date.

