13.2 Primary analysis

The IRR and corresponding 95% CIs will be used to compare the malignancy events among the efgartigimod exposed cohort vs. the reference cohort. The calculations will be performed separately for each individual database and across all three (3) databases as a meta-analysis according to published methods.

A quasi-Poisson regression model will be used to estimate the incidence rate ratio between cohorts with number of event occurrences as the response variable, cohort and age as covariates and follow-up time as offset. Scale/overdispersion parameter will be used to account for potential over- or under-dispersion.

In addition, the balance of baseline measures, including matching variables (i.e. age, sex, CCI and duration of previous MG treatment) and other demographic and disease characteristics, will be assessed. The imbalanced measures which are considered to be potential confounders based on clinical judgement will be added to the quasi-Poisson model as additional covariates.

- Age will be adjusted as a covariate in the quasi-Poisson model to account for the increased malignancy risk over time, no matter balanced or not. And age-specific incidence rates and incidence rate ratio between cohorts can be calculated.
- Concomitant and/or previous use of monoclonal antibody will be adjusted as a covariate in the quasi-Poisson model to account for any potential imbalance.

The primary analyses will be performed on an “as-treated” basis. To this end, patients will contribute person time until the first occurrence of the following events: death, loss to follow-up, end of study period, or a switch from any MG treatment to efgartigimod (for the reference cohort). For the analyses performed based on “as-treated” basis, the time before switching to efgartigimod for the reference cohort will be counted toward the overall person-time but not the time after switching.

A sensitivity analysis based on the intention-to-treat principle will be conducted to ensure the continued monitoring of safety outcomes, irrespective of any treatment modifications throughout the follow-up period. For the sensitivity analyses performed based on “intent-to-treat” basis, both the time before and after switching will be counted. Sensitivity analysis will be described as noted in section 13.5.

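### The power of over 85% in Section 11 treats the between-database variance as known; with that variance estimated from three databases, no usual random-effects test gives both 5% error and the stated power

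*Protocol*

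**What the plan says.** Section 11 (Study size) works in two steps. First, one pooled comparison as if all patients came from a single database: "Using a two-sided inequality test for two (2) Poisson rates", "with 5% significance level, >85% power and rate ratio 1.3 under alternative hypothesis". This gives 679 efgartigimod patients. Section 9.1 supplies the allocation: "efgartigimod initiators will be matched 2:1 (reference: efgartigimod").

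Second, an allowance for heterogeneity. The reason begins: "Since the variation under a random-effect model assuming heterogeneity across databases consists of both within-database and between-database variation". With an assumed I² of 0.5, the 679 is multiplied by 1/(1 − I²) = 2. The result: "A total of 1358 efgartigimod-treated patients are needed with a rate ratio of 1.3 under alternative hypothesis", stated for "6-year follow-up and background rate of 42.0 per 1,000 PY to achieve >85% power".

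The text before Table 4 adds: "Table 4 shows that there are >80% power in most scenarios under the adjusted sample size of 1358". For the base scenario Table 4 prints 86.13%. The paragraph before Table 5 compares the anticipated 1,599 patients with 1,358 and concludes that power will be satisfactory. The abstract attaches a power of over 80% to the same 1,358. Section 13.2 says only that results will be combined "across all three (3) databases as a meta-analysis according to published methods".

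**The concern.** Doubling the sample size compensates for a larger variance. It does not deal with that variance being unknown. The cut-off of 1.96 is right when the between-database variance is a given number. Here it has to be estimated from three log rate ratios, and three values say very little about a variance.

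The cost appears either as error above 5%, if the normal cut-off is kept, or as lower power, if the cut-off is widened. Section 11 claims the nominal level and the full power together, and uses the claim to set the minimum cohort and to declare the study feasible. Malignancy is an important potential risk in the EU risk management plan. A reader of the final report may therefore weigh a pooled interval that includes 1 against a stated power of 86%, or take an interval that excludes 1 as having a 5% false-alarm rate.

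**Working it through.** **Inputs (Sections 9.1 and 11).** Reference rate 0.042 per person-year; follow-up 6 years; rate ratio 1.3; two reference patients per efgartigimod patient; two-sided 5%; I² = 0.5; N = 679 unadjusted and 1,358 adjusted; three databases, anticipated split 522 / 477 / 600 (Table 5).

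**Step 1: reproduce the plan's figure.** For n efgartigimod patients the variance of the log rate ratio is V = 1/E₁ + 1/E₀, where E₁ and E₀ are the expected events.
- n = 679: E₁ = 679 × 6 × 0.042 × 1.3 = 222.4; E₀ = 1,358 × 6 × 0.042 = 342.2.
- V = 1/222.4 + 1/342.2 = 0.00742; SE = 0.0861.
- ln(1.3)/SE = 0.2624/0.0861 = 3.046.
- Power = Φ(3.046 − 1.960) = 86.1%, matching Table 4.

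The six rows of Table 3 also reproduce within tolerance.

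**Step 2: what 86% means at 1,358.** Doubling n halves the within-database variance to 0.00371. I² = 0.5 doubles the total back to 0.00742, so the standardised effect is again 3.046. The printed power is thus a normal test at 1,358 with doubled and known variance. Simulation with the variance known gives 86% power and 5.0% error. With no heterogeneity, 1,358 patients would have ln(1.3)/√0.00371 = 4.308 and power of about 99.1%.

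**Step 3: how well three databases estimate the variance.** With three equal databases, each has within-variance 3 × 0.00371 = 0.0111. I² = 0.5 makes τ² equal to that, so τ is about 0.105. Cochran's Q then follows 2 × χ² with 2 df. The DerSimonian-Laird estimate is zero when Q ≤ 2, which has probability 1 − exp(−0.5) = 39%. In about four analyses in ten, the estimated heterogeneity is nil although the true I² is 0.5.

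**Step 4: power and error with the variance estimated.** N = 1,358, rate ratio 1.3, I² = 0.5. Simulations used 200,000 to 400,000 three-database meta-analyses.

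| Test | Type I error | Power |
|---|---|---|
| Variance known, cut-off 1.96 (the protocol's case) | 5.0% | 86% |
| DerSimonian-Laird, cut-off 1.96 | about 9.5% | about 82% |
| DerSimonian-Laird, cut-off 2.37 (set for 5% at I² = 0.5) | 5.0% | about 73% |
| Hartung-Knapp, t with 2 df, cut-off 4.30 | 5.0% | about 40% |

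The Hartung-Knapp value agrees with a direct calculation: noncentral t, 2 df, noncentrality 3.046, critical value 4.303, giving 39.6%. Using the Table 5 split or Poisson counts moves it by less than one point. At N = 1,599 the noncentrality is 3.306 and power is 44%. At N = 1,358, power is about 82% for a rate ratio of 1.6 if I² is held at 0.5, and about 80% if τ is held at its base value.

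The cut-off of 2.37 holds 5% only while I² does not exceed 0.5. Its error rises to about 9% at I² = 0.75 and 13% at 0.9.

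**Step 5: other Table 4 rows at rate ratio 1.3, N = 1,358, Hartung-Knapp.** The answer depends on what is held fixed.

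| Rate per 1,000 PY, years | Table 4 | I² held at 0.5 | τ held at 0.105 |
|---|---|---|---|
| 42.0, 6 | 86.13% | 40% | 40% |
| 42.0, 8 | 94.03% | 48% | 43% |
| 60.0, 6 | 95.36% | 50% | 44% |
| 60.0, 8 | 98.76% | 60% | 48% |
| 73.6, 6 | 98.17% | 57% | 47% |
| 73.6, 8 | 99.67% | 67% | 50% |

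**The case against.** The strongest reply is that nothing is miscalculated. The tables reproduce, the assumption I² = 0.5 is stated openly, the inflation factor is cited, and treating a nuisance variance as known is an ordinary planning approximation. That stands as far as the arithmetic goes. But the approximation is harmless only when the variance will be well estimated, which three databases do not allow.

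A second reply is that the pooling test is not named, that naming it is ordinary SAP content, and that Hartung-Knapp is a debatable choice with three studies. It has only about 62% power even when I² is zero, so much of its loss comes from the 2 df cut-off. This also stands. A reader might infer that the study has 40% power and would miss a 30% increase 60% of the time. The documents do not support that as a general statement, because both figures belong to Hartung-Knapp in the base scenario. With a conventional DerSimonian-Laird interval the miss rate is about 18%, and the problem is false alarms.

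A third reply is that Section 11 calls the analysis exploratory, with no hypothesis to confirm or reject. That limits the consequence. It does not excuse the figure, since power is what the protocol uses to set the minimum cohort and claim feasibility.

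None of these replies produces a usual test with both 5% error and over 85% power under Section 11's own assumptions.

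**Conclusion.** The point holds as a misstatement of power, not as an arithmetic slip. Section 11 commits to random effects, I² = 0.5, a two-sided 5% level and over 85% power at 1,358 patients. Once the between-database variance is estimated from three databases, the tests examined give about 82% power at about 9.5% error, about 73% at 5% error if I² is exactly 0.5, or about 40% at 5% error without knowing I².

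These figures rest on 42.0 per 1,000 person-years, 6 years, a rate ratio of 1.3, normally distributed database effects and I² = 0.5. They do not show that the cohort is too small for an exploratory study, nor that the protocol must prescribe Hartung-Knapp. It would also be wrong to rescue 86% by calling it the homogeneous case at 1,358: that is about 99%, and 86.1% is the homogeneous power of 679 patients.

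**What to change.** In Section 11, Table 4 and the abstract:
- State that the printed power assumes a known between-database variance.
- Add power, with type I error, for a random-effects test that estimates the variance from three databases. For the base scenario: Hartung-Knapp about 40% at a rate ratio of 1.3 (about 44% at 1,599 patients) and about 80% near 1.6, with the DerSimonian-Laird figures alongside (about 82% at about 9.5% error; about 73% when recalibrated at I² = 0.5).
- If other Table 4 rows are recomputed, say whether I² or τ is held fixed.
- If a homogeneous case is shown, give 86.1% for 679 patients and about 99% for 1,358.

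In the paragraph before Table 5, drop or qualify the conclusion that power is satisfactory. The pooled-interval method can be named in the SAP, but a normal-quantile DerSimonian-Laird interval should not be described as having 5% error with three databases.

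The cost is wording and one recalculated table, with a less favourable power statement. No additional patients or data are needed.
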